The 6MWT is a submaximal exercise test during which the distance walked (6MWD), oxygen saturation, systemic BP, heart rate, and the degree of dyspnea and fatigue (Borg CR10 Scale) are evaluated. The 6MWT provides an indirect estimate of aerobic capacity and correlates with pulmonary vascular hemodynamics. In particular, 6MWD is directly correlated with cardiac index increase and inversely correlated with PVR decrease [Savarese, G., et al 2013]. The use of the change in 6MWD as a primary endpoint in clinical trials is based on findings from studies which demonstrated that increases in 6MWD are associated with improved clinical outcomes among patients with PAH. A clinically meaningful 6MWD increase of 30 to 50 meters is considered predictive of better long-term prognosis and reflects positively in patient-important outcomes, such as HRQoL [Mathai, S. C., et al 2012] [Divers, C., et al 2017]. Change in 6MWD at Week 12 will be the primary efficacy endpoint of the Base Period of the Phase 3 Cohort. The change in 6MWD will be a secondary efficacy endpoint for the Phase 2 Cohort Base Period at Week 12 and for the Extension Period of Phase 3 Cohort at Week 24, and an exploratory endpoint for the Phase 2 Cohort Extension Period at Week 24.

Time to Clinical Worsening

TTCW is a composite endpoint of morbidity and mortality in a time-to-event analysis [Sitbon, O., et al 2015] [Pulido, T., et al 2013] [Galie, N., et al 2015]. The components of this composite endpoint include death, PAH-related hospitalization, and disease progression.

WHO Functional Class

The WHO classification of functional status is a measure of disease severity, based on a patient's description of their level of functioning and symptoms of disease in relation to their everyday activity. Patients are assigned 1 of 4 WHO-FC, dependent on limits of physical activity. As WHO-FC increases from I to IV, limits of physical activity increase. WHO-FC is a predictor of survival, both before and during treatment [Waxman, A. B. 2015], and remains an important part of the ongoing assessment of patients with PAH. Improvement in WHO-FC predicts survival independently of PAH cause or time of diagnosis. Furthermore, changes in

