Multiplicity	There are 3 treatment group comparisons that may be tested to address the primary hypothesis. Testing will be done in a sequential manner in descending order of MK-5475 randomized dose group, stopping at the point statistical significance is not achieved.		
Sample Size and Power	The planned sample size is approximately 164 participants. For the percent change from baseline in PVR at Week 12, the study has 85% power to demonstrate that MK-5475 380 μ g is superior to placebo group at an overall one-sided 2.5% alpha level.		

Phase 3 Cohort

Study Design Overview			
Treatment Assignment	 Participants (approximately 143/group) will be randomized in a 1:1 ratio between 2 treatment groups: 1) MK-5475 2) placebo matching MK-5475 		
Analysis Populations	Efficacy: FAS Safety: APaT		
Primary Endpoint	Change from baseline in 6MWD at Week 12		
Key Secondary Endpoints	N/A		
Statistical Methods for Key Efficacy Analyses	The difference (MK-5475 minus placebo) in change from baseline and the associated 95% CI and p -value will be provided based on a robust regression model. Missing 6MWD observations at Week 12 from participants in both treatment groups will be imputed based on the observed 6MWD observations at Week 12 from the placebo group.		
Statistical Methods for Key Safety Analyses	For analyses in which 95% CIs will be provided for between- treatment differences (MK-5475 minus placebo) in the percentage of participants with events, these analyses will be performed using the M&N method.		
Interim Analyses	No interim analyses are planned. (The primary analysis of efficacy data from the Phase 3 Cohort will occur when all participants in this cohort have completed [or discontinued prior to the end of] the Base Period. Although the Phase 3 Cohort will continue in the study [in the Extension Period], the Base Period analysis is not considered an interim analysis.)		
Multiplicity	As there is a single hypothesis test involving a single endpoint and a single between-treatment comparison, no multiplicity adjustment is required.		
Sample Size and Power	The planned sample size is approximately 286 participants. For the change from baseline in 6MWD at Week 12, the study has 90% power to demonstrate that MK-5475 is superior to placebo group at a one-sided 2.5% alpha level.		

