9.4.2 Phase 3 Cohort Efficacy Endpoints

Primary Efficacy Endpoint

• Mean change from baseline in 6MWD at Week 12

Secondary Efficacy Endpoint

- Mean change from baseline in 6MWD at Week 24
- Proportion of participants whose WHO-FC is not worse at Week 12 relative to baseline

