The difference (MK-5475 minus placebo) in percent change from baseline and the associated 95% CI and *p*-value will be provided. A *p*-value for the comparison of MK-5475 versus placebo <0.025 (one-sided) will be considered statistically significant contingent upon the multiplicity strategy (Section 9.8).

The following steps will be taken to perform the primary analysis, including imputation for missing data. Percent change from baseline in PVR at Week 12 is the response variable:

- 1. Define imputation model for different missingness patterns:
 - a. Obtain the worst outcome among all observed data.
 - b. Within the placebo group, for participants with both baseline and Week 12 data, fit an ANCOVA model including terms for treatment and WHO-FC (Class II and Class III/IV).

- 2. Impute missing data for different missingness patterns:
 - a. Death: for participants (in both treatment groups) who died before Week 12, the worst outcome among all observed data will be used to impute the missing Week 12 values.
 - b. Reasons other than death: For participants (in both treatment groups) missing the response variable, the fitted model in Step 1 will be used to impute the missing values.
- 3. Robust regression based on a Huber-type M estimator [Huber, P. J. 1973] will be performed for the imputed dataset. The model will include terms for treatment and WHO-FC (Class II and Class III/IV).
- 4. Steps 2 and 3 will be repeated 50 times to create 50 complete datasets and 50 sets of parameter estimates.
- 5. The final parameter estimate for the mean percent change will be the average of the 50 parameter estimates for the mean percent change from Step 4.
- 6. Steps 1 through 5 will be repeated 200 times based on bootstrap resampling. The resulting standard error for the mean percent change will be the standard error of the resulting parameter estimates obtained in the 200 bootstrap resampled datasets. The CI and *p*-value will be derived from a normal distribution based on the final parameter estimate and its standard error.

Two sensitivity analyses for percent change from baseline in PVR will be performed to assess the impact of missing data imputation. Within the same PMM structure in the primary analysis, for missing data due to reasons other than death, 1 analysis will use a tipping point approach and the other analysis will use an approach referred to as washout imputation.

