The difference in change from baseline and the associated 95% CI and *p*-value will be provided (MK-5475 minus placebo). A *p*-value for the comparison of MK-5475 versus placebo <0.025 (one-sided) will be considered statistically significant.

The following steps will be taken to perform the primary analysis, including imputation for missing data. Percent change from baseline in 6MWD at Week 12 is the response variable:

- 1. Define imputation model for different missingness patterns:
 - a. Obtain the worst outcome among all observed data.
 - b. Within the placebo group, for participants with both baseline and Week 12 endpoint, an MMRM model including terms for treatment and WHO-FC (Class II and Class III/IV) will be fit.
- 2. The same procedure in Steps 2 through 6 described in Section 9.6.1.1 will be used for analysis.

Two sensitivity analyses of the estimand for change from baseline in 6MWD will be performed to assess the impact of missing data imputation. Within the same PMM structure in the primary analysis, for missing data due to reasons other than death, 1 analysis will use a tipping point approach and the other analysis will use an approach referred to as washout imputation. The analysis approaches are the same as in the 2 sensitivity analyses described in Section 9.6.1.1 except the missing data due to reasons other than death will be imputed by the MMRM model in the primary analysis.

As a supplemental analysis, the primary analysis will be repeated, excluding participants who participated in the Phase 2 Cohort.

Secondary Endpoint

The primary approach for addressing the mean change from baseline in 6MWD at Week 24 will use the same robust regression method in Section 9.6.1.1. Summary statistics will be provided for the proportion of participants whose WHO-FC is not worse at Week 12 relative to baseline. Table 6 summarizes the analysis strategy for efficacy endpoints in the Phase 3 Cohort.

Endpoint	Туре	Statistical Method	Analysis Population	Missing Data Approach
Primary Endpoint				
Change from baseline in 6MWD at Week 12	P Sen Sen	RR RR RR	FAS FAS FAS	PMM-J2R PMM-Tipping point PMM-Washout
Secondary Endpoints				
Change from baseline in 6MWD at Week 24	Р	RR	FAS	PMM-J2R
Proportion of participants whose WHO functional class does not worsen at Week 12 relative to baseline.	Р	SS	FAS	N/A

Table 6	Analysis Strategy for Primary and Secondary Efficacy Endpoints in the Phase
	3 Cohort

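### The Phase 3 primary analysis steps name percent change in 6MWD as the response variable, while the endpoint, estimand summary and sample size use change in metres

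*Combined protocol and SAP*

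**What the plan says.** Section 9.6.1.2 opens the Phase 3 primary analysis steps with "Percent change from baseline in 6MWD at Week 12 is the response variable". After defining the imputation model it adds "The same procedure in Steps 2 through 6 described in Section 9.6.1.1 will be used for analysis". The two last imported steps, in Section 9.6.1.1, read "The final parameter estimate for the mean percent change will be the average of the 50 parameter estimates" and "The resulting standard error for the mean percent change will be the standard error of the resulting parameter estimates".

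Elsewhere the Phase 3 primary endpoint is an absolute change:

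- Section 4.2.1.1: "Change in 6MWD at Week 12 will be the primary efficacy endpoint of the Base Period of the Phase 3 Cohort".
- Section 9.1, Phase 3 summary: "The difference (MK-5475 minus placebo) in change from baseline and the associated 95% CI".
- Section 9.4.2: "Mean change from baseline in 6MWD at Week 12".
- Section 9.6.1.2: the estimand's population-level summary is the mean change. The contrast announced just before the steps is "The difference in change from baseline and the associated 95% CI". Table 6 lists change from baseline.
- Section 9.9.1: a true effect of 30 m, 27 m after jump-to-reference imputation, and an SD of 70 m.

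On death, both estimands (Sections 9.6.1.1 and 9.6.1.2) declare a hypothetical strategy, meaning the Week 12 value had the participant not died. The analysis in both cohorts gives participants who died the worst observed outcome.

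**The concern.** The step list is the part of the plan that gets programmed, and it is the only detailed algorithm for the single Phase 3 hypothesis. A programmer working from it would analyse percent change; one working from Table 6 would analyse metres. Each could claim to follow the prespecified plan, so the scale could be settled after results are known.

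The scale affects more than the units of the report. The worst outcome used for deaths, the placebo-based imputed values and the tipping-point adjustment are all defined on the response variable. For illustration, a loss of 100 m from a 500 m baseline is the worse result in metres (100 m against 60 m). A loss of 60 m from a 150 m baseline is the worse result in percent (40% against 20%). A treatment difference in percentage points also could not be compared with the 27 m planning effect or with the threshold of more than 30 m that Section 9.9.1 calls clinically relevant.

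The death handling raises a separate, lesser question. Assigning the worst value treats death as a bad outcome, which is a composite-type approach. It does not estimate what the value would have been without the death.

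**Working it through.** **1. Which scale was the cohort sized on?** Inputs from Section 9.9.1: difference 27 m, SD 70 m, 143 per group, one-sided alpha 0.025. The 70 m is taken as the per-arm SD of change.

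- SE = 70 × √(2/143) = 8.28 m
- 27 / 8.28 = 3.26
- Power = Φ(3.26 − 1.96) = 90.3%; noncentral t with 284 df gives 90.2%
- n per group for 90% = 2 × (70/27)² × (1.960 + 1.282)² = 141.3, rounded up to 142

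The stated 90% at 143 per group reproduces in metres. Section 9.9.1 words the 70 m as the SD of a between-group difference. Read literally, that gives SE = 70/√143 = 5.85 m and power Φ(27/5.85 − 1.96), about 99.6%, so the per-arm reading is the one that was used. No effect, SD or baseline mean is given in percent, so power on that scale cannot be derived from the documents.

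**2. Are the two variables interchangeable?** Inclusion criterion 5 allows a baseline 6MWD of 150 to 500 m. A 27 m gain is 27/150 = 18.0% at the bottom of that range and 27/500 = 5.4% at the top, so they are not.

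**3. How much does the choice matter?** Simulation: 143 per group, change drawn from N(0, 70) or N(27, 70) metres, assumed normal baselines truncated to 150–500 m (realised means 306 to 389 m), Huber regression on treatment only, complete data, model-based SE, 3,000 trials per row.

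| Assumed baseline (mean, SD), m | Power, metres | Power, percent | Verdicts that differ |
|---|---|---|---|
| 300, 90 | 88.6% | 87.7% | 3.5% |
| 320, 90 | 88.0% | 86.8% | 3.1% |
| 350, 80 | 89.1% | 88.4% | 2.5% |
| 375, 75 | 88.9% | 88.3% | 2.5% |
| 400, 70 | 89.2% | 88.9% | 2.2% |

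The constant 27 m effect becomes about 7.1 to 9.1 percentage points.

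A second simulation let effect and SD scale with baseline and used a simple difference in means (4,000 trials per case). Power was 86.9% in metres and 89.5% in percent with uniform baselines on 150–500 m. It was 89.5% and 90.8% with N(350, 80) baselines clipped to that range. Which scale has more power therefore depends on how the effect varies with baseline.

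**4. Death handling.** The documents give no death rate, so counts are assumed. Same Huber set-up in metres, effect 27 m, deaths set to the lowest observed change in either arm, 3,000 trials per case (Monte Carlo SE about 0.16 m). The estimate with no deaths is 26.9 m.

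| Deaths | Placebo only | Same number in each arm | MK-5475 only |
|---|---|---|---|
| 1 | 28.1 m | 27.1 m | 26.1 m |
| 3 | 29.6 m | 26.6 m | 24.4 m |
| 5 | 31.1 m | 27.0 m | 22.8 m |

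**The case against.** The strongest reply is that this is an evident slip. The sentence has the same form as the PVR sentence in Section 9.6.1.1. The lines around it in Section 9.6.1.2 say change from baseline, every endpoint statement agrees, and the sample size is in metres. On this view only one reading is plausible, and the numerical consequence is small in any case. The first part is probably right about how the line arose, and the second is right about size. Neither resolves the text: the wrong variable stands in the operative steps of a confirmatory test, and nothing in the plan overrides it.

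Other objections stand in part:

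- The percent wording of imported Steps 5 and 6 is not independent evidence. It is the Phase 2 phrasing of a general procedure, which the plan also reuses for other 6MWD endpoints labelled as change. It needs restating but adds no separate contradiction.
- The simulations leave out WHO functional class, imputation and the bootstrap SE, and they rest on assumed baselines. They indicate size only, and no loss of power is established.
- The 27 m used there is the diluted planning effect. The assumed true effect is 30 m.
- The death mismatch is a separate and lesser matter. It is unquantified for PVR, and changing Phase 2 handling raises a timing problem, because Phase 2 Base Period results are unblinded to choose the Phase 3 dose.

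**Conclusion.** The concern holds. As written, the plan gives two response variables for its only confirmatory Phase 3 test, and the one in the step list disagrees with every other statement of that endpoint. It must be corrected because the primary variable has to be unambiguous before unblinding. No material loss of power has been shown: the two scales differ by at most 1.2 points in the Huber simulations, and verdicts differ in 2.2% to 3.5% of trials, all under assumed baselines. The sample size is sound on the metre scale.

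The death mismatch is also real but of lower severity. With five deaths confined to one arm the estimate moves to about 22.8 m or 31.1 m, depending on the arm. With balanced deaths the shift is negligible. These figures depend wholly on the assumed counts.

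**What to change.** **Main change.** In Section 9.6.1.2, replace the response-variable line so that it names change from baseline in 6MWD at Week 12, in metres. Add a note that, wherever the Section 9.6.1.1 procedure is applied to 6MWD, the parameter in Steps 5 and 6 is the mean change in metres. The note should also cover the Phase 2 Week 12 and Phase 3 Week 24 6MWD analyses, which reuse the method.

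**Secondary change.** Make the death strategy and the computation agree, in one of two ways:

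- Declare a composite strategy, include death in the definition of the variable, and say whether the worst outcome means the worst change or the worst Week 12 value.
- Keep the hypothetical strategy, impute deaths with the model used for other missing data, and move worst-value imputation to a sensitivity analysis. This needs a statement of whether the hypothetical value is on or off treatment, because jump-to-reference draws from placebo.

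For the Phase 2 Cohort, change the computation only if its Base Period data are still blinded. Otherwise keep the computation and correct the label.

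**Cost.** A short protocol amendment before Phase 3 unblinding. Section 9 requires an amendment for methods tied to primary hypotheses and limits the supplemental SAP to exploratory and other non-confirmatory analyses. No new data are needed and the sample size is unchanged.

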In the Phase 3 Cohort Base Period, participants will take part in the study for approximately 16 weeks, including a screening period of up to 4 weeks and a 12-week double-blind treatment period. Approximately 286 eligible participants will be randomized in a 1:1 ratio to MK-5475 and placebo. Participants will be instructed to inhale 1 dose per day, in the morning, for 84 consecutive days. 6MWD will be measured, using the same procedure as for the baseline measurement, every 4 weeks and at the end of Phase 3 Cohort Base Period. All participants will continue treatment in an Extension Period until a requisite number of clinical worsening events are observed in the Phase 3 Cohort and a second Phase 3 study. The second Phase 3 study will be described in a separate protocol. A separate integrated analysis plan will be written, providing more details. A CAC, whose members are blinded to the study group assignments, will review all reported clinical events and adjudicate the clinical events related to clinical worsening (See Appendix 1).

In both Phase 2 and Phase 3 Cohorts, additional hemodynamic parameters, changes in symptoms, biomarkers, and participant self-rated quality-of-life questionnaire scores will be used to evaluate response to treatment throughout the study.

Selected members of the Sponsor study team and management will be unblinded to results from Phase 2 Cohort Base Period and Phase 3 Cohort Base Period, to evaluate the efficacy and safety profile of MK-5475 (Section 9.7). For the Phase 2 Cohort Extension Period and Phase 3 Cohort Extension Period, separate blinded Sponsor study teams will monitor the ongoing study.

For each cohort, the double-blind treatment period concludes with a final visit. All participants will complete a telephone follow-up visit 14 days (+ 2 days) after the final visit, for AE monitoring.

AEs will be monitored throughout the study and graded in severity according to the guidelines outlined in Section 10.3.4. Regular safety assessments will be performed during the study (Section 8.3.9).

To supplement the routine trial monitoring outlined in this study, an external DMC will monitor interim data (Section 9.7).

Specific procedures to be performed during the study, including prescribed times and associated visit windows, are outlined in Section 1.3 of the SoA. Details of each procedure are provided in Section 8.

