9.6.1.2 Phase 3 Cohort

In the Phase 3 Cohort, efficacy endpoints will be collected during the Base and Extension Periods. For the Base Period, the analysis timepoint of interest is Week 12. For the Extension Period, the analysis timepoint of interest is Week 24. Summary statistics will be provided for every planned data collection timepoint described in the SoA (Section 1.3).

Primary Endpoint

The primary estimand for the primary objective used for the Phase 3 Cohort contains 5 attributes:

- The treatment condition of interest is MK-5475 or matching placebo on background stable concomitant PAH-specific therapy, as defined in Section 5.1.
- The population of participants targeted by the clinical question are male/female participants with PAH between the ages of 18 and 75 years (inclusive).
- The variable to address the clinical question is 6MWD at Week 12.
- The following are intercurrent events, along with the approaches to handle them:
 - Death: hypothetical strategy to evaluate 6MWD at Week 12 as though death would not occur.

• Treatment discontinuation: treatment policy strategy seeking to use every participant's actual Week 12 value, regardless of whether they are still taking study medication.

The approach to handling missing data for these intercurrent events is described below.

• The population-level summary is mean change from baseline in 6MWD at Week 12.

For this estimand, the primary approach will use a robust regression method to address the primary hypothesis. Robust regression method will be used because change from baseline in 6MWD is not expected to follow a normal distribution, based on other Phase 3 clinical trials which have used non-parametric methods for analyzing 6MWD [Rubin, L. J., et al 2002] [Rubin, L. J., et al 2015]. The robust regression model will include a term for treatment and WHO-FC (Class II and Class III/IV). Missing 6MWD observations at Week 12 from participants in all treatment groups will be imputed following a PMM. Missing data due to death will be imputed based on the worst outcome among all observed data. Missing data due to treatment discontinuation will be imputed based on the observed 6MWD observations at Week 12 from the placebo group referred as J2R (detailed below). If there are missing Week 12 data for other reasons, J2R will also be used. The randomization seed for imputations will be 5475007.

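### The Phase 3 imputation model is called an MMRM but, as specified, is a single-visit placebo-completer model that does not use dropouts' own Week 4 and Week 8 6MWD

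*Combined protocol and SAP*

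**What the plan says.** Section 9.6.1.2 (Phase 3, primary analysis) defines the imputation model in Step 1b, within the placebo group: "for participants with both baseline and Week 12 endpoint, an MMRM model including terms for treatment and WHO-FC". The sentence introducing the steps names one time point: "Percent change from baseline in 6MWD at Week 12 is the response variable". (It says percent change, whereas the endpoint is change in metres. That is a separate inconsistency.) The paragraph before it says that missing values after treatment discontinuation, and for other non-death reasons, are "imputed based on the observed 6MWD observations at Week 12 from the placebo group", under the label J2R. Step 2 then borrows Steps 2 to 6 of Section 9.6.1.1, where for reasons other than death "the fitted model in Step 1 will be used to impute the missing values". Deaths take the worst observed outcome. There are 50 imputations and 200 bootstrap resamples.

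Section 4.1 says that Phase 3 6MWD is measured "every 4 weeks and at the end of Phase 3 Cohort Base Period", and Section 8.2.2 schedules the walk test at all Phase 3 site visits. Weeks 4 and 8 are therefore collected.

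The Phase 2 counterpart in Section 9.6.1.1 is to "fit an ANCOVA model including terms for treatment and WHO-FC (Class II and Class III/IV"), also within placebo only. For the Phase 3 Week 24 secondary endpoint, the plan "will use the same robust regression method in Section 9.6.1.1".

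**The concern.** An MMRM uses several visits per participant and borrows from earlier visits when a later one is missing. The model in Step 1b has the name but not the ingredients. If a programmer follows the words, a participant whose 6MWD had fallen well below the arm mean by Week 8 and who then stopped attending is imputed from placebo participants who reached Week 12, matched only on WHO-FC. If a programmer follows the label, the same participant's decline carries into the imputed value. The two readings can give different primary estimates in the confirmatory cohort, and the plan does not settle which applies.

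The planned sensitivity analyses do not resolve this. Section 9.6.1.2 says that both use the MMRM of the primary analysis for non-death missingness. The tipping-point analysis shifts its imputations. The washout analysis uses it for placebo and takes its residual spread for MK-5475. Neither is said to bring in the earlier visits.

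**Working it through.** **1. Planned figure.** Inputs from Section 9.9.1: true effect 30 m, dropout 10% per arm, SD 70 m, 143 per group, one-sided alpha 0.025.
- Effect after J2R: 30 × (1 − 0.10) = 27 m.
- 27 / (70 × √(2/143)) = 3.26, and Φ(3.26 − 1.96) = 90.3%. The stated 90% reproduces.
- Required n = 2 × (1.960 + 1.282)² × 70² / 27² = 141.3, so 142 against the stated 143.

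**2. The model as listed.** Within placebo the design columns are an intercept, a constant treatment column and a WHO-FC indicator. The rank is 2 of 3, so treatment is not estimable. With one Week 12 response per participant and no visit or baseline term, what remains is a mean per WHO-FC stratum plus residual spread. This is the same structure as the Phase 2 ANCOVA.

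**3. What the two readings do to the contrast.** The documents give no visit correlation, selection strength or unequal dropout rates, so these are assumptions. Let d_T and d_P be the dropout proportions (MK-5475, placebo), D_T and D_P the mean Week 8 shortfall of dropouts below their own arm, and r the Week 8 to Week 12 correlation.
- Literal rule: dropouts in both arms get the placebo completers' mean, which lies s = r × d_P × D_P / (1 − d_P) above the full placebo mean.
- J2R conditional on history: dropouts get the placebo mean minus r × D.
- Gap in the contrast (literal minus conditional) = d_T × (r × D_T + s) − s.

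If the log-odds of dropout rise by 1 per SD (70 m) of Week 8 shortfall, then D = 62.7, 57.2 and 52.6 m at 5%, 10% and 15% dropout. Example, 15% MK-5475 / 5% placebo, r = 0.5: s = 0.5 × 0.05 × 62.7 / 0.95 = 1.65, and gap = 0.15 × (0.5 × 52.6 + 1.65) − 1.65 = +2.5 m.

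The simulated gaps come from 1,500 trials per scenario (143 per arm, arm means only, no Huber step or bootstrap).

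| MK-5475 / placebo dropout | Selection | Gap, r = 0.5: formula (simulated) | Gap, r = 0.8: formula (simulated) |
|---|---|---|---|
| 10% / 10% | none | 0 (−0.04) | 0 (−0.02) |
| 10% / 10% | same in both | 0 (−0.02) | 0 (−0.04) |
| 15% / 5% | same in both | +2.54 (+2.53) | +4.07 (+4.04) |
| 5% / 15% | same in both | −2.84 (−2.80) | −4.55 (−4.56) |
| 10% / 10% | MK-5475 only | +2.86 (+2.83) | +4.58 (+4.43) |
| 10% / 10% | placebo only | −2.86 (−2.88) | −4.58 (−4.49) |

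In the second row each arm mean is 3 to 5 m higher under the literal rule, but the shift cancels in the difference. A separate large-sample simulation with correlation 0.75 gave 29.22 against 25.27 m (+3.95) for 15% / 5%, and 24.37 against 28.66 m (−4.29) for 5% / 15%. Halving its selection slope reduced the gaps to about 2.1 to 2.4 m.

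**The case against.** The strongest reply is that earlier visits were intended. Phase 2 PVR has one post-baseline catheterization and gets an ANCOVA. Phase 3 6MWD is repeated, and the plan switches to an MMRM and repeats that choice for the sensitivity analyses. A list of included terms need not be complete. This stands to the extent that no sentence excludes Weeks 4 and 8. A reader might infer that the plan deliberately discards them, but the documents support only that, as written, no step uses them.

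Other points also stand:
- The gap compares two imputation rules and is not bias against a known truth. Conditioning on history removes only the bias that observed visits explain. Unseen decline after the last visit remains, and participants lost before Week 4 have no history to use.
- Stopping treatment is not itself missing data. Section 8.11.5 brings participants who discontinue in the Base Period back at Week 12 for all Visit 6 procedures, which should limit how many values are imputed.
- A reader might picture every dropout set to one average value. The 50 imputations and the seed imply random draws, made within WHO-FC stratum, and deaths follow their own rule.
- For Week 24, the cross-reference concerns the robust regression method, and Table 6 lists the missing-data approach separately. It can be read as importing the single-visit ANCOVA, but not with certainty. Secondary p-values are nominal (Section 9.6).

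None of this supplies the missing visits, terms and covariance structure, or makes the treatment term estimable.

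**Conclusion.** The Phase 3 primary imputation model is internally inconsistent and underspecified, and its literal reading leaves collected Week 4 and Week 8 data unused. The rank problem and the missing elements follow from the text without assumptions.

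At the planned 10% dropout per arm with like selection, the effect on the contrast is essentially zero. A reader might infer that the sample size is wrong or that the rule favours MK-5475. The documents support neither: 143 per group and 90% reproduce, and the shift can go either way. If dropout rate or selection differs by arm, the estimate moves by roughly 2 to 4.6 m, which is about 7% to 17% of 27 m. Equal dropout rates alone do not protect the contrast if selection differs. These sizes rest on assumed correlations of 0.5 to 0.8, assumed selection on Week 8 6MWD, and assumed 15%/5% or 5%/15% dropout or one-arm selection.

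This should be corrected before unblinding, because it leaves a programmer to choose between two primary estimates.

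**What to change.** In Section 9.6.1.2 Step 1b:
- Fit the MMRM to all placebo FAS participants with any post-baseline 6MWD, at Weeks 4, 8 and 12.
- Include visit, WHO-FC and baseline 6MWD, and no treatment term. State the covariance structure. Unstructured with visit interactions is one reasonable choice, not the only one.
- State that J2R imputation conditions on each participant's own observed visits.

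For Week 24, state that the same model extended to Week 24 is used, in place of the bare reference to Section 9.6.1.1. In Section 9.6.1.1, delete the treatment term from the placebo-only ANCOVA. This is tidying only, because imputed values do not change once the term drops out.

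The cost is wording and standard reference-based imputation code, with no new data. Because this concerns the method for a primary hypothesis, the opening of Section 9 calls for a protocol amendment before unblinding. The supplemental SAP route there covers exploratory and other non-confirmatory analyses.
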